## I. LIST OF ABBREVIATIONS AND KEY TERMS

### List of Abbreviations

Abbreviations	Description of abbreviations
AE	Adverse event
ALP	Alkaline phosphatase
ALT	Alanine aminotransferase (GPT)
ANCOVA	Analysis of covariance
API	Astellas Pharma Inc.
AST	Aspartate aminotransferase (GOT)
CI	Confidence interval
CRF	Case report form
Dev	Development
eCRF	Electronic case report form
FAS	Full analysis set
H	High
ICGI	Investigator-rated clinical global impression
ICH	International Conference on Harmonization of Technical Requirements for Registration of Pharmaceuticals for Human Use
IRLS	International restless legs scale
ISN	International study number
L	Low
LOCF	Last observation carried forward
MAR	Missing at random
MCMC	Markov chain Monte Carlo
MedDRA	Medical dictionary for regulatory activities
MI	Multiple imputation
MMRM	Mixed model of repeated measurements
MNAR	Missing not at random
N	Normal
PCGI	Patient-rated clinical global impression
PD	Pharmacodynamic
PK	Pharmacokinetics
PMM	Pattern mixture model
PPS	Per protocol set
PSQI	Pittsburgh sleep quality index
PT	Prothrombin time (second)
QOL	Quality of life
RLS	Restless legs syndrome
SAE	Serious adverse event
SAF	Safety analysis set
SAS	Statistical Analysis Software
SD	Standard deviation
SOC	System organ class
TEAE	Treatment-emergent adverse event
TLF	Tables, Listings and Figures
ULN	Upper limit of normal
WHODDE	WHO drug dictionary enhanced

### List of Key Terms

Term	Definition of terms
Follow-up period	The period from the start of administration of the study drug for the follow-up period to the final observation
Gabapentin	An antiepileptic drug synthesized in Germany in 1973; the active metabolite of gabapentin enacarbil
Gabapentin enacarbil	The active substance of Regnite Tablets; nonproprietary name of the drug
Registration failure	A subject who provided informed consent but did not fulfill the inclusion/exclusion criteria for formal registration and thus was not randomized or did not receive open-label study drug, or who withdrew consent during the run-in period.
Study period	The period from informed consent of the subject to completion of protocol-specified last evaluation/observation in the subject
Screening	A process of active consideration of potential subjects for enrollment in the study, conducted during the run-in period to determine the eligibility for the study
Enroll	To register or enter a patient into a clinical trial as a subject; NOTE: Once a subject is enrolled into the study, the clinical study protocol applies to the subject.
Subject	Study participant
Subject ID number	A number assigned to a subject who provided consent to participate in the study by signing the consent form
Endpoint	An attribute, phenomenon, or event that varies in quality or quantity and serves as a variable
Baseline	Measurement or finding obtained at a time point judged to be initiation of observation for comparison
Run-in period	The period from the start of administration of the study drug for the run-in period to before the start of administration of the study drug for the treatment period
Randomization	A process of assigning study subjects to treatment or control groups in which an element of chance is used in the determination of assignments to reduce bias
Regnite® Tablets	Alternative name for the study drug gabapentin enacarbil; brand name of the drug product approved for marketing in January 2012
ASP8825	Alternative name for the study drug gabapentin enacarbil; a drug substance code used by Astellas Pharma Inc.
GSK1838262	Alternative name for the study drug gabapentin enacarbil; a drug substance code used by GlaxoSmithKline K.K.
XP13512	Alternative name for the study drug gabapentin enacarbil; a Drug substance code used by XenoPort, Inc.

## **1 INTRODUCTION**

[figure not shown]
This Statistical Analysis Plan (SAP) contains a more technical and detailed elaboration of the principal features of the analysis described in the protocol, and includes detailed procedures for executing the statistical analysis of the primary and secondary endpoints and other data.

The SAP is finalized and signed prior to unblinding.

This statistical analysis is coordinated by the responsible biostatistician of Dev, API. Any changes from the analyses planned in the SAP will be justified in the Clinical Study Report (CSR).

## 2 FLOW CHART AND VISIT SCHEDULE

### Flow Chart

- \* Subjects using the following drugs before the start of the run-in period will require the specified washout period:
  1. Dopamine agonists, dopamine preparations, gabapentin, pregabalin:  $\geq 7$  days
  2. Opioids, benzodiazepines (for only if used to treat RLS), long-acting dopamine agonists:  $\geq 14$  days
- \*\* For the subjects discontinued during the treatment period, the tests/observations required at discontinuation will be performed and then post-treatment follow-up will be performed as far as possible, but this does not require the use of placebo during the follow-up period.

< Start and end of the post-marketing clinical study >

The time of the start of this post-marketing clinical study is defined as the time at which informed consent is obtained from the first subject. The time of the end of this post-marketing clinical study is defined as the time at which protocol-specified final assessment is implemented in the last subject.

## Schedule of Assessments

	Run-in period	Treatment period									Follow-up period	Discontinuation *5
		W-1	W0	W1	W2	W4	W6	W8	W10	W12		
Day of observation	-7		1	8	15	29	43	57	71	85	Last dosing of the study drug for the treatment period + 8 days *4	
Allowed visit window	-10 to -7		1	5 to 11	12 to 18	26 to 32	40 to 46	54 to 60	68 to 74	82 to 88	Last dosing of the study drug for the treatment period + 5 to 11 days *4	
Visit	●	●	●	●	●	●	●	●	●	●	●	●
Informed consent	●											
Subject characteristics	●											
Assessment against inclusion/exclusion criteria	●	●										
Patient registration	● Provisional	● Formal										● Discontinuation
Prescription of the study drug	●	●	● *3	●	●	●	●	●	●	●		
Compliance status		●	●	●	●	●	●	●	●	●	●	●
Concomitant medication monitoring	●	●	●	●	●	●	●	●	●	●	●	●
IRLS score	●	●	●	●	●	●	●	●	●	●	●	●
ICGI		●	●	●	●		●	●	●	●	●	●
PCGI		●	●	●	●		●	●	●	●	●	●
Pittsburgh Sleep Quality Index		●			●		●		●			●
Athens Insomnia Scale		●			●		●		●			●
EQ-5D-5L		●			●		●		●			●
RLS Pain score	●	●	●	●	●	●	●	●	●	●	●	●
Epworth Sleepiness Scale		●	●	●	●	●	●	●	●	●	●	●
Laboratory tests	◎	◎		◎	◎		◎		◎		◎	◎
Thyroid function tests (TSH, Free T 4 )			◎						◎			◎
HbA1c	◎											
Ferritin	◎											
Estimated creatinine clearance	●											
Pregnancy test *1	●								●			●
Height	●											
Body weight	●	●			●		●		●			●
Vital signs	●	●	●	●	●	●	●	●	●	●		●
Adverse event monitoring *2	●	●	● *3	●	●	●	●	●	●	●	●	●

◎Central measurements

\* Not required in men, postmenopausal women (no menstruation for at least 1 year), or other women with a history of hysterectomy, bilateral oophorectomy, etc. in whom a possibility of pregnancy is clearly excluded.

\* A medical interview should determine any occurrence of eye disorders such as blurred vision or accommodation disorder.

\* In subjects with an estimated creatinine clearance of  $\geq 60$  to  $< 90$  mL/min at the start of the run-in period randomized to the gabapentin enacarbil group, in whom the dose is titrated from 300 mg to 600 mg, any occurrence of AEs should be carefully assessed and the subject's condition should be adequately observed, based on which whether the subject can continue with the study should be carefully determined.

\* Follow-up observation will occur on the day of "last dosing of the study drug for the treatment period +8 days," which will be Day 92 in subjects who take the study drug for the treatment period up to Day 84 per protocol.

\* For the subjects discontinued during the run-in period, the compliance status and any AEs will be investigated.

For the subjects discontinued during the treatment period, the tests/observations required at discontinuation will be performed, and then post-treatment follow-up (i.e., the Week 13 procedure) will be performed as far as possible, but this does not require the use of placebo during the follow-up period.

For the subjects discontinued during the follow-up period, the Week 13 procedure will be performed as the tests/observations at discontinuation.

### **3 STUDY OBJECTIVE AND DESIGN**

#### **3.1 Study Objective**

- To verify the efficacy of oral gabapentin enacarbil 600 mg once daily compared with placebo on the basis of the change from baseline in IRLS score in patients with moderate to severe idiopathic restless legs syndrome (RLS), using a multicenter, randomized, double-blind, parallel-group, comparative design.
- To evaluate the safety of gabapentin enacarbil 600 mg.

#### **3.2 Study Design**

Gabapentin enacarbil 600 mg or placebo will be administered orally once daily after the evening meal. Patients meeting the inclusion and exclusion criteria at provisional registration will receive single-blind placebo for 1 week (run-in period). Of these, patients meeting the inclusion and exclusion criteria at formal registration will be randomized to receive double-blind treatment with either gabapentin enacarbil 600 mg or placebo for 12 weeks (treatment period). After the end of the 12-week treatment period, single-blind placebo will be given for 1 week (follow-up period) for follow-up observation.

However, of the patients meeting the inclusion and exclusion criteria at formal registration, those with an estimated creatinine clearance of  $\geq 60$  to  $< 90$  mL/min at the start of the run-in period will receive randomized double-blind treatment initially with either gabapentin enacarbil 300 mg or placebo for 1 week (upward titration period) followed by gabapentin enacarbil 600 mg or placebo for 11 weeks, totaling 12 weeks (treatment period including the upward titration period).

#### **3.3 Randomization**

The person responsible for study drug randomization will prepare the treatment codes for randomization of the study drug for the double-blind period, and retain them under lock and key until the time of treatment code breaking.

Stratified allocation will be performed with stratification factors of age ( $< 50$  years and  $\geq 50$  years) at the start of the run-in period and estimated creatinine clearance ( $\geq 60$  to  $< 90$  mL/min and  $\geq 90$  mL/min) at the start of the run-in period, to minimize imbalance in subject characteristics between the treatment groups to allow for proper comparison. The patient registration center will assign the drug numbers to the subjects in accordance with the patient registration procedures.

### **4 SAMPLE SIZE**

180 subjects per group (360 subjects in the two groups) as participants in the treatment period.

[Rationale for sample size]

The Japanese phase II/III study [CL-0003] demonstrated the change in IRLS score (mean and standard deviation) at the end of treatment period (Week 12) as shown in Table 1. Of the randomized subjects, 11.8% in the placebo group and 17.5% in the 600 mg group were discontinued during the treatment period.

**Table 1: Change in IRLS score (mean and standard deviation) at the end of treatment period (i.e., Week 12 of study treatment) in the Japanese phase II/III study [CL-0003]: FAS**

	Placebo		ASP8825 600 mg	
	N	Mean (SD)	N	Mean (SD)
Week 12 (LOCF)	116	-8.96 (7.286)	120	-11.10 (7.921)
Week 12 (Treatment period completers)	105	-9.27 (6.996)	98	-11.54 (7.793)

SD: Standard Deviation. LOCF: Last Observation Carried Forward

In addition, a repeated measures analysis of variance of the data from the patients given placebo or ASP8825 600 mg in the Japanese phase II/III study [CL-0003] and included in the Full Analysis Set showed that the adjusted means of the change from baseline in IRLS score at the end of treatment period (Week 12) were -9.15 in the placebo group and -11.71 in the 600 mg group. The difference between the adjusted means from the two groups was -2.56.

On the basis of these results, the difference between treatment groups in the change from baseline in IRLS score at the end of treatment period (Week 12) as the primary endpoint of this study was assumed to be -2.56, with a standard deviation of 8.000 in both groups. Under these assumptions, to detect a statistically significant difference between gabapentin enacarbil and placebo using a 2-sample t-test with a two-sided significance level of 0.05 and a power of 80%, 155 subjects per group would be required. Assuming the discontinuation rate during the treatment period was approximately 15.0% in each group, the sample size has been set to 180 per group.

## **5 ANALYSIS SETS**

In principle, the analysis sets below will be used. However, the final decision on handling of cases for analyses will be made in a case review before the treatment code breaking, in light of opinions/advice from medical expert, statistical advisor, and others.

### **5.1 Full Analysis Set (FAS)**

The Full Analysis Set (FAS) will consist of all subjects who received the study drug for the treatment period and were evaluated for at least one efficacy (either primary or secondary) endpoint during the treatment period. The FAS will be the primary analysis set for efficacy analyses.

### **5.2 Per Protocol Set (PPS)**

The Per Protocol Set (PPS) will consist of the subjects in the FAS who meet the following criteria:

- Subjects meeting the inclusion criteria
- Subjects not meeting any of the exclusion criteria that can affect efficacy assessments
- Subjects not using excluded concomitant medications or therapies that can affect efficacy assessments
- Subjects given the study drug for the treatment period for at least 2 weeks from the start of the treatment period
- Subjects with  $\geq 70\%$  compliance with study treatment during the treatment period

### **5.3 Safety Analysis Set (SAF)**

The Safety Analysis Set (SAF) will consist of all subjects given at least one dose of the study drug for the treatment period.

## **6 ANALYSIS VARIABLES**

### **6.1 Efficacy Endpoints**

#### **6.1.1 Primary Efficacy Endpoint**

Change from baseline in IRLS score at the end of treatment period (Week 12)

#### **6.1.2 Secondary Efficacy Endpoints**

The secondary efficacy endpoints are as follows:

- Change from baseline in IRLS score at each time point
- ICGI responder rate at each time point
- PCGI responder rate at each time point
- Change from baseline in Pittsburgh Sleep Quality Index at each time point
- Change from baseline in Athens Insomnia Scale at each time point
- Change from baseline in RLS Pain score at each time point
- Change from baseline in EQ-5D-5L at each time point

##### **6.1.2.1 ICGI and PCGI**

In terms of Investigator-rated Clinical Global Impression (ICGI) and Patient-rated Clinical Global Impression (PCGI), a subject with “Very much improved” or “Much improved” is defined as “Responder”; otherwise, “Non-responder”.

##### **6.1.2.2 Pittsburgh Sleep Quality Index**

The Pittsburgh Sleep Quality Index (PSQI) is a self-administered questionnaire to assess subjective sleep quality during the previous month (see [Appendix 1: Pittsburgh Sleep Quality Index](#)). The self-rated items of the PSQI generate seven component scores (range of subscale scores, 0-3): sleep quality, sleep latency, sleep duration, habitual sleep efficiency, sleep disturbance, use of sleeping medication, and daytime dysfunction. The sum of these seven component scores yields one global score of subjective sleep quality (range, 0-21); higher scores represent poorer subjective sleep quality. For more details and description of the component and global scores, refer to [Appendix 1: Pittsburgh Sleep Quality Index](#)

### **6.1.2.3 EQ-5D-5L**

The EQ-5D-5L is an international standardized non-disease specific (i.e. generic) instrument for describing and valuing health status, and a multi-dimensional measure of health-related QOL.

EQ-5D-5L includes two main components: (1) a VAS scale rating perception of overall health and (2) 5 qualitative domains: Mobility, Self-Care, Usual Activities, Pain/Discomfort, and Anxiety/Depression. No imputation will be performed in case of a missing item.

## **6.2 Safety Variables**

Safety will be assessed by evaluation of the following variables:

- Vital signs
- Adverse events
- Laboratory tests
- Body weight
- Epworth Sleepiness Scale

### **6.2.1 Adverse Events**

TEAE is defined as an adverse event observed after starting administration of the study drug in the treatment period. If the adverse event occurs on the date of first dose of study drug (treatment period) and the onset check box is marked “ONSET BETWEEN FIRST DOSE OF STUDY DRUG IN TREATMENT PERIOD AND FIRST DOSE OF STUDY DRUG IN FOLLOW UP PERIOD”, then the adverse event will be considered treatment-emergent.

A drug-related TEAE is defined as any TEAE with at least possible relationship to study treatment as assessed by the investigator or with missing assessment of the causal relationship.

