2.2.2 Dose Rationale

[Rationale for the dosage]

The dosage and administration stated in the Japanese package insert for Regnite Tablets is “The usual adult dose for oral use is 600 mg (as gabapentin enacarbil) once daily after dinner.” However, the efficacy of gabapentin enacarbil 600 mg was not verified by the primary analysis of the Japanese phase II/III study [CL-0003]. Thus, this study has been planned to verify the efficacy of gabapentin enacarbil 600 mg/day and also to evaluate the safety.

The mode and duration of administration have been set to once daily for 12 weeks, as in the Japanese phase II/III study [CL-0003]. Gabapentin enacarbil is considered to require dose adjustment according to renal function, because it is a renally excreted drug, and Japanese and overseas studies in patients with renal impairment showed prolonged elimination half-life and increased Cmax and AUCinf of gabapentin (active metabolite of gabapentin enacarbil) in plasma in association with impaired renal function. Thus, for patients with an estimated creatinine clearance of ≥ 60 to < 90 mL/min at the start of the run-in period, a 1-week upward titration period for administration at the starting dose of 300 mg has been employed with reference to the package insert, aiming to verify the efficacy of 600 mg/day while securing the safety of the subjects. A 1-week run-in period has been set to confirm the eligibility against the inclusion and exclusion criteria at formal registration. A 1-week follow-up period has been set to check for withdrawal symptoms after the end of administration of the study drug in the treatment period.

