5.5 Adverse Events and Other Safety Aspects

5.5.1 Definition of Adverse Events (AEs)

An AE is any untoward medical occurrence in a subject, temporally associated with the use of the study drug, whether or not considered related to the medicinal product. An AE can therefore be any unfavorable and unintended sign (including an abnormal laboratory finding), symptom, or disease (new or exacerbated) temporally associated with the use of the study drug.

For AEs noted during the run-in period, the event term, event onset date, time to event onset, event end date, severity, seriousness, other actions taken, and outcome will be entered on the eCRF.

For AEs noted during the treatment period, the event term, event onset date, time to event onset, event end date, severity, seriousness, action taken with the study drug, other actions taken, outcome, causal relationship to the study drug for the treatment period, and basis for the causality assessment will be collected and entered on the eCRF. However, the basis for the causality assessment will be required on the eCRF only for SAEs, AEs leading to discontinuation, and other AEs for which description of the basis is requested by the sponsor. In addition, as necessary, the investigator will record details of the treatment and clinical course in an appropriate document.

AEs during the follow-up period will also be collected, and the event term, event onset date, time to event onset, event end date, severity, seriousness, action taken with the study drug, causal relationship to the study drug for the treatment period, basis for the causality assessment, other actions taken, and outcome will be entered on the eCRF. However, the basis for the causality assessment will be required on the eCRF only for SAEs, AEs leading to discontinuation, and other AEs for which description of the basis is requested by the sponsor. In addition, as necessary, the investigator will record details of the treatment and clinical course in an appropriate document.

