#### **7.5.1 Adverse Events**

An overview table will include the following details:

- Number of TEAEs,
- Number and percentage of subjects with TEAEs,
- Number of drug related TEAEs,
- Number and percentage of subjects with drug related TEAEs,
- Number of serious TEAEs,
- Number and percentage of subjects with serious TEAEs,
- Number of serious drug related TEAEs,
- Number and percentage of subjects with serious drug related TEAEs,
- Number of TEAEs leading to withdrawal of treatment,
- Number and percentage of subjects with TEAEs leading to withdrawal of treatment,
- Number of drug related TEAEs leading to withdrawal of treatment,
- Number and percentage of subjects with drug related TEAEs leading to withdrawal of treatment, and
- Number of deaths.

The number and percentage of subjects with TEAEs, as classified by SOC and PT will be summarized for each treatment group. Summaries will be provided for:

- TEAEs,
- Drug related TEAEs,
- Serious TEAEs,
- Serious drug related TEAEs,
- TEAEs leading to withdrawal of treatment,
- Drug related TEAEs leading to withdrawal of treatment,
- TEAEs excluding serious adverse event that equal to or exceed a threshold of 5.0% in any treatment group,
- Common TEAEs that equal to or exceed a threshold of 5.0% in any treatment group,
- Common drug related TEAEs that equal to or exceed a threshold of 5.0% in any treatment group.

The number of TEAEs and the number and percentage of subjects with TEAEs, as classified by SOC and PT will also be summarized by severity and by relationship to study drug. In the subject count, if a subject has multiple TEAEs with the same SOC or PT, but with differing severity or relationship, then the subject will be counted only once with the worst severity or highest degree of relationship, however, if any of the severity or relationship values are missing then the subject will be counted only once with missing severity or relationship. In the adverse event count, the adverse events will be presented in each category they were classified to. Drug related TEAEs will be presented in a similar way by severity only.

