The number and percentage of subjects with TEAEs, as classified by SOC and PT will be summarized by time interval. For each adverse event in a particular interval, a subject will be counted if there is an onset of TEAEs regardless of onset in other intervals. Time intervals will be categorized according to the following categories (days from the first dosing of study drug in the treatment period):

- $\geq 1$  (0 weeks) to  $\leq 29$  (4 weeks)
- $> 29$  (4 weeks) to  $\leq 57$  (8 weeks)
- $> 57$  (8 weeks) to  $\leq 85$  (12 weeks)
- $> 85$  (12 weeks)

The number and percentage of subjects with TEAEs, as classified by SOC and PT will be summarized by subgroups defined in section 7.8.

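### No adverse-event output is anchored to the last treatment-period dose, so the follow-up week set to check for withdrawal symptoms is reported only partly and indirectly

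*SAP*

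**What the plan says.** Protocol 2.2.2 states why the follow-up week exists: "A 1-week follow-up period has been set to check for withdrawal symptoms after the end of administration of the study drug in the treatment period". Protocol 5.5.1 has the matching data collected: "AEs during the follow-up period will also be collected, and the event term, event onset date, time to event onset, event end date, severity, seriousness", together with causality to the treatment-period drug.

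The SAP's safety tables are built on one definition, in 6.2.1: "TEAE is defined as an adverse event observed after starting administration of the study drug in the treatment period". It has a start and no end. The same section mentions an eCRF onset category, "ONSET BETWEEN FIRST DOSE OF STUDY DRUG IN TREATMENT PERIOD AND FIRST DOSE OF STUDY DRUG IN FOLLOW UP PERIOD", but uses it only to classify events on the date of the first treatment-period dose.

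SAP 7.5.1 tabulates TEAEs in an overview, by SOC and PT, by severity, by relationship and by subgroup. None of these tables is divided at the end of dosing. One table is divided by time: "Time intervals will be categorized according to the following categories (days from the first dosing of study drug in the treatment period"), with cuts at Days 29, 57 and 85. SAP 7.5.1.1 adds a Kaplan-Meier plot of time to first somnolence or dizziness. It also starts at the first treatment-period dose, and event-free completers are censored at their last evaluation.

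For the rating scales, SAP 7.10.3 defines a Follow-up analysis visit 5 to 11 days after the last treatment-period dose for IRLS, RLS Pain, ICGI/PCGI and Epworth. SAP 7.4.2 and 7.5.5 summarise these by arm and visit or time point.

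**The concern.** Withdrawal symptoms are defined by time since the last dose. An output that counts from the first dose, or does not use time at all, can separate them from on-treatment events only when treatment length happens to line up with its cut-points. Treatment length varies here, because the Week 12 visit window spans seven days and some subjects stop early.

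Two things are at stake. The question the follow-up week was added to answer has no adverse-event table designed for it. And off-drug events enter the main TEAE profile of the randomised arm, which blurs the on-treatment safety picture of 600 mg, the second study objective (Protocol 2.1). The blurring need not be equal between arms: in CL-0003, 11.8% of the placebo group and 17.5% of the 600 mg group discontinued (SAP 4).

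**Working it through.** The plan states no figure for this point. The check is whether any adverse-event output separates time on drug from time off drug.

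**Inputs.** A subject dosed to Day 84 has follow-up on Day 92, so the nominal post-drug span is 92 − 84 = 8 days (Schedule of Assessments, note 4). The Week 12 visit window is Day 82 to 88, so I take completers' last doses as Day 81 to 87, the day before the visit. The AE intervals are those of SAP 7.5.1. I assume the first treatment-period dose is on Day 1, so that study day and days from first dosing agree.

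**Formula.** For a last dose on Day D, the post-drug days are D+1 to D+8. The number falling in the interval above Day 85 is 0 if D ≤ 77, D − 77 if D is 77 to 85, and 8 if D ≥ 85. The number of on-drug days in that interval is max(0, D − 85).

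| Last dose | Post-drug days | Of 8, at or below Day 85 | Of 8, above Day 85 | On-drug days above Day 85 |
|---|---|---|---|---|
| Day 40 | 41–48 | 8 | 0 | 0 |
| Day 77 | 78–85 | 8 | 0 | 0 |
| Day 80 | 81–88 | 5 | 3 | 0 |
| Day 81 | 82–89 | 4 | 4 | 0 |
| Day 82 | 83–90 | 3 | 5 | 0 |
| Day 83 | 84–91 | 2 | 6 | 0 |
| Day 84 | 85–92 | 1 | 7 | 0 |
| Day 85 | 86–93 | 0 | 8 | 0 |
| Day 86 | 87–94 | 0 | 8 | 1 |
| Day 87 | 88–95 | 0 | 8 | 2 |

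The follow-up visit may fall 5 to 11 days after the last dose. The latest stop whose whole post-drug span lies at or below Day 85 is then Day 80 (80 + 5 = 85) to Day 74 (74 + 11 = 85), with Day 77 at the nominal 8 days.

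**How many subjects stop early.** At the assumed rate, 15% × 180 = 27 per arm. At the CL-0003 rates, 11.8% × 180 = 21.2 for placebo and 17.5% × 180 = 31.5 for 600 mg. These are upper figures for misplaced post-drug weeks, because:
- follow-up of discontinuers is done only as far as possible;
- lost subjects contribute nothing;
- late stoppers fall partly above Day 85.

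**Other outputs.** The remaining AE tables have no time axis. The Kaplan-Meier plot runs past the end of dosing without marking it. The scales have summaries at Follow-up, and an End of treatment analysis visit is also defined. But changes are taken from Week 0 only, so no paired End of treatment to Follow-up change is produced. Comparing mean scores at Week 12 and Follow-up is not a substitute: Week 12 is a fixed-day window, while Follow-up is timed from last dose and can include early stoppers.

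**The case against.** A reader might infer that no planned output could show a withdrawal effect. The documents do not support that. For a completer dosed to Day 84, the interval above Day 85 lies wholly after treatment and is tabulated by SOC and PT. Dosing is in the evening, so much of Day 85 is still within a day of the last dose, and losing that day matters little.

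Nor is it right that a symptom which occurs on drug and recurs on stopping leaves no trace. A recurrence is a new AE (Protocol 5.5.1), and the interval table's rule is "For each adverse event in a particular interval, a subject will be counted if there is an onset of TEAEs regardless of onset in other" time bands. A completer's recurrence after Day 85 is therefore counted again there. SAP 7.5.1 also gives event counts by severity and relationship.

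Nor are the scales shown only as change from Week 0. Raw IRLS, RLS Pain and Epworth scores are summarised and plotted by arm and visit, and IRLS and RLS Pain have between-arm differences by visit. A marked mean rebound at Follow-up would be visible, and change from Week 0 is the natural measure of rebound above baseline.

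An open-ended TEAE definition is also a legitimate choice, consistent with collecting causality to the treatment-period drug for follow-up events. Withdrawal is not a listed objective or endpoint, and the table and listing specifications are in a separate document not available here.

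All of this stands, and it limits the point. What remains is that the interval above Day 85 matches the withdrawal window only through the timing of completion. It generally misses early stoppers, and no denominator of subjects observed after last dose is stated.

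**Conclusion.** The point holds in limited form. No adverse-event output in the SAP is anchored to the last treatment-period dose, although the protocol set the follow-up week to check for withdrawal symptoms. The interval above Day 85 is a fair proxy at the scheduled last dose (7 of 8 post-drug days). It weakens across the visit window (4 of 8 for Day 81; 1 or 2 on-drug days mixed in for Days 86 and 87) and fails for stops by Day 77. Early stoppers of any timing number up to about 27 of 180 per arm at the assumed 15%, or about 21 and 32 at the CL-0003 placebo and 600 mg rates. Their post-drug events fall mostly among on-treatment events.

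These figures rest on a first dose on Day 1, a nominal 8-day post-drug span, and follow-up being obtained. The documents give no rate of withdrawal events, so the effect on the safety results cannot be sized. The primary efficacy analysis is not affected.

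**What to change.** Keep the overall TEAE tables and add the following to SAP 6.2.1 and 7.5.1:

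- **Split.** Use the Analysis Date of Last Dose in Treatment Period, already defined in SAP 6.3.1. Events with onset up to and including that date are on-treatment; later onsets are post-treatment. Assign events on the last-dose date to on-treatment by rule. The eCRF onset category cannot resolve them, because its boundary is the first follow-up dose, which early discontinuers need not take.
- **Table.** Tabulate post-treatment events by SOC, PT and arm. Use subjects observed after the last treatment-period dose as the denominator, and show completers and early discontinuers separately. The SAP 7.2.1 population dosed in follow-up would be too narrow, for the same reason.
- **Scales.** Add within-subject change from End of treatment to Follow-up for IRLS, RLS Pain and Epworth. State that the two values must be different assessments, since the End of treatment window (to last dose + 7 days) overlaps the Follow-up window (from last dose + 5 days).

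The cost is SAP wording and a few extra tables. Dates and follow-up scores are already collected.
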